8.1.2 Establishing Year 1 Reference Standard

Positive Breast Cancer Status for Screening Year 1 is established if one of the following is true:

- A participant has a histopathologic diagnosis of breast cancer^a within the time period from Year 1 screening^b until Year 2 screening^c, not including Year 2 screening
- A participant does not undergo Year 2 screening^c but has a histopathologic diagnosis of breast cancer^a within 365 days of Year 1 screening.

Negative Breast Cancer Status for Screening Year 1 is established by any of the following, in order of best to least reliable determination:

1. A participant has both Year 2 screening MBI and DBT, both with negative or benign findings, or positive findings that are ultimately determined to be benign after diagnostic imaging workup or tissue diagnosis.
2. A participant does not complete both Year 2 screening MBI and DBT, but is followed through chart review or patient contact, resulting in documentation of any breast imaging test performed at least 335 days after Year 1 screening, with negative or benign findings, or positive findings that are ultimately determined to be benign after diagnostic imaging workup or tissue diagnosis.
3. A participant does not undergo Year 2 screening but is contacted at least 335 days after Year 1 screening and the participant herself confirms that she did not have a breast cancer diagnosed that meets the Positive Breast Cancer Status definition.
4. A participant does not undergo Year 2 screening but is followed through chart review at least 335 days after Year 1 screening and no breast cancer is reported to meet the Positive Breast Cancer Status definition.

A participant with breast cancer detected on Year 2 screening is assumed to have negative breast cancer status for Year 1 and the cancer diagnosis is included in the Year 2 analysis, not the Year 1 analysis.

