8.2.2 Establishing Year 2 Reference Standard

Positive Breast Cancer Status for Screening Year 2 is established if one of the following is true:

- A participant has a histopathologic diagnosis of breast cancer^a within the time period from Year 2 screening until the next annual screen (Year 2), not including the next annual screen.
- A participant does not undergo Year 2 screening^d but has a histopathologic diagnosis of breast cancer within 365 days of Year 2 screening.

Negative Breast Cancer Status for Screening Year 2 is established by any of the following, in order of best to least reliable determination:

1. A participant is followed through chart review or patient contact, resulting in documentation of any breast imaging test performed at least 335 days after Year 2 screening, with negative or benign findings, or positive findings that are ultimately determined to be benign after diagnostic imaging workup or tissue diagnosis.
2. A participant does not undergo Year 2 screening^d but is contacted at least 335 days after Year 2 screening and the participant herself confirms that she did not have a breast cancer diagnosed that meets the Positive Breast Cancer Status definition.
3. A participant does not undergo Year 2 screening^d but is followed through chart review at least 335 days after Year 2 screening and no breast cancer is reported to meet the Positive Breast Cancer Status definition.

A participant with breast cancer detected on Year 2 screening is assumed to have negative breast cancer status for Year 2.

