8.1.3 Participants Not Meeting Reference Standard Definitions

If a participant does not meet either definition for Positive or Negative Breast Cancer Status in a given screening year, for instance a participant who has no known breast cancer diagnosis but has no information available via chart review and cannot be contacted, will be considered “lost to follow up” and assumed to not have breast cancer in the analysis. In the event of a participant’s death, the date of death and cause of death will be recorded to determine if breast cancer was diagnosed and the length of follow up.

^aThe date of histopathologic breast cancer diagnosis is defined as the date on which tissue was obtained via biopsy or surgical excision, and subsequently determined to include invasive cancer (with or without DCIS) or DCIS.

^bYear 1 screening is defined as having both Year 1 MBI and Year 1 DBT. If not performed on the same day, the date of Year 1 screening is the day Year 1 MBI is performed.

^cYear 2 screening is targeted to be performed with both MBI and DBT approximately 365 days (target range 335 – 455 days) after Year 1 screening MBI. For purposes of establishing breast cancer status of Screening Year 1, Year 2 screening may be performed with any combination of breast imaging tests, most often including MBI, DBT, or both, but may also include breast MRI, WBUS, or CEDM; testing may be performed for either screening or diagnostic indications. The date of Year 2 screening used for reference standard is the earliest of these tests performed at least 335 days after Y0 screening.

^dYear 2 screening is not conducted as part of the research study, but considered for purposes of establishing Year 2 breast cancer status as any documentation of breast imaging (MBI, DBT, MRI, WBUS, or CEDM) performed within 335 – 455 days after Year 2 screening.

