8.3 Definitions of Screening Test Results

The result of either screening exam (DBT or MBI) on a patient with no cancerous lesions can be either true negative (TN) or false positive (FP). The per-patient score will be defined as the higher score between the two breasts or, if there are multiple scored findings within a breast, the maximum score within the patient.

1. A TN test result will be defined as a negative test score on a patient with a negative reference standard. For DBT, a negative BI-RADS score will be 1 or 2; a negative test score on MBI will be a score of 1 or 2 on the 5-point assessment scale.
2. A FP test result will be defined as a positive test score on a patient with a negative reference standard (BI-RADS 0, or BI-RADS 3 or higher for DBT; 3 or higher on the MBI assessment scale).

The result of either exam on a patient with at least one cancer can be either true positive (TP) or false negative (FN).

1. A TP test result will be defined as a positive test score and correct localization of the lesion on a patient with a positive reference standard.
 - a. Correct localization will be determined by an expert radiologist reconciler as follows: A DBT or MBI finding will be deemed to correspond with a cancer (invasive or DCIS) if it is located in the same quadrant of the breast and at the same depth (anterior, middle, or posterior, if recorded on the pathology report).
 - b. Any cancer found by pathologic analysis that does not have a matching DBT or MBI finding will be considered occult (false-negative) on that modality.
 - c. Any DBT or MBI finding that does not match with a cancer on the pathology report will be considered in the analysis as a false-positive.
 - d. Two or more discrete cancerous lesions identified on pathology may be deemed to match a single DBT or MBI finding if the lesions correspond in location with a larger imaging finding (e.g., the pathology report describes several small adjacent masses in a single quadrant, where on imaging, a single larger region in that quadrant is

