8.6 Secondary Endpoints

- 1. To compare the rate of detection of invasive cancers between DBT alone vs. MBI alone at Year 1 screening.**

The comparison will be based on a 2-sided McNemar's test at statistical significance level alpha= 0.05.

2. To compare the screening performance metrics of sensitivity, specificity, recall rate, biopsy rate, positive predictive value and negative predictive value for DBT and MBI.

For both years of the study imaging (Year 1 and Year 2), the following secondary endpoints will be analyzed to compare performance of

- DBT alone vs. MBI alone, and
- DBT alone vs. the combination of DBT with supplemental MBI.

Sensitivity will be estimated for each modality as the proportion of women with breast cancer who have true positive test results. **Specificity** will be estimated as the proportion of women without breast cancer who have TN test results. Uncertainty in the estimate of sensitivity will be quantified through a two-sided 95% confidence interval (CI) based on the binomial distribution. If a sufficient number of radiologists interpret exams from multiple patients with breast cancer, secondary analysis may also include a 95% CI and chi-squared test adjusted for clustering of results within radiologist to allow generalization to both the population of patients and the population of radiologists.³⁶ For comparisons of DBT alone vs. the combination of DBT with supplemental MBI, a structural zero results due to the paired nature of the data and direct comparisons cannot be tested under a null hypothesis of equivalence. Analysis will alternatively focus on the conditional diagnostic odds ratio (cDOR) to quantify the added value of MBI over DBT alone.

Recall rate (defined as the proportion of patients recalled from the screening test for diagnostic workup among the total number of patients screened), and **biopsy rate** (defined as the proportion of patients in whom biopsy is generated from a particular modality among the total number of patients screened) will be estimated employing analytical strategies similar to sensitivity and specificity. McNemar's test will be used to compare rates between two modalities.

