5. To assess the rate of interval cancers with incorporation of MBI screening.

For the purpose of our analysis, interval cancers are defined as cancers diagnosed not at study imaging but between Year 1 and Year 2 screening tests. The interval cancer rates per 1000 women screened will be determined as the proportion of participants in the analysis set who had an interval cancer diagnosed and verified by pathology. To assess whether the incorporation of MBI screening, with one year of follow-up for breast cancer results in a “low” interval cancer rate, we will compare the interval cancer rate found in our study to the reported interval cancer rates for a population of women with dense breasts.

Per Breast Cancer Surveillance Consortium (BCSC) analysis³⁸ the interval cancer rate among women with dense breasts was 89 per 100,000 women (or ~0.9 per 1000). The authors of this analysis considered an interval cancer rate greater than 1 case per 1000 mammography examination as an unacceptable performance level. We will estimate the rate of interval

cancers from our study and provide a 95% confidence interval. The performance level of this screening approach will be considered unacceptable if the lower bound of the confidence interval exceeds 1/1000 (i.e. 7 or more interval cancers in this cohort).

6. To examine the relative performance of DBT and MBI within subgroups categorized by breast cancer risk.

The comprehensive risk factor collection planned in this study will allow accurate risk estimation promoting generalizability of results by type of risk model and level of risk. As an exploratory analysis, we will examine if the risk estimates determined with Gail, BCSC, Claus, and Tyrer-Cuzick models may predict a subgroup of women with MDB who are more likely to benefit from a specific supplemental screening. In particular, the relative performance of the screening modalities (sensitivity and specificity) will be characterized separately, within subgroups of patients defined by various levels of risk. The statistical power to discern differential performances of the screening modalities among different risk subgroups may be limited due to the restricted sample size in these subgroup analyses.

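### Section 8.2.2 makes a cancer detected at Year 2 screening both positive and negative for Year 2, so the Year 2 accuracy measures have no single definition

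*Combined protocol and SAP*

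**What the plan says.** Three provisions of the combined protocol and SAP decide the status of a woman whose cancer is found at the second study round.

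- Section 8.1.2, last sentence: she is negative for Year 1, and "the cancer diagnosis is included in the Year 2 analysis, not the Year 1 analysis".
- Section 8.2.2, first positive criterion: she is positive for Year 2 if tissue diagnosis falls "within the time period from Year 2 screening until the next annual screen (Year 2), not including the next annual screen".
- Section 8.2.2, closing sentence: "A participant with breast cancer detected on Year 2 screening is assumed to have negative breast cancer status for Year 2".

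The footnotes under section 8.1.3 bear on the labels. Footnote d describes a Year 2 screening that is outside the study and takes place 335 to 455 days after Year 2 screening. Footnote c dates the Year 2 screening used for the reference standard: it "is the earliest of these tests performed at least 335 days after Y0 screening". No Y0 is defined anywhere else.

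Section 8.3 builds the test results on this status, and section 8.6 item 2 uses them in both rounds: "For both years of the study imaging (Year 1 and Year 2), the following secondary endpoints will be analyzed".

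**The concern.** The reference standard decides who counts as having cancer. If the closing sentence of 8.2.2 is followed, a cancer found at the second round is negative for Year 1 under 8.1.2 and negative for Year 2 under 8.2.2. It then counts in neither year, although 8.1.2 says it belongs to Year 2.

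At stake are the Year 2 measures that need cancer status: sensitivity, specificity, PPV1, NPV and the conditional diagnostic odds ratio, for DBT alone, MBI alone and the combination. Screen-detected cancers would move from true positive or false negative to false positive or true negative. A cancer seen only on MBI would become a true negative for DBT, which overstates the NPV of DBT alone. While the text stands, someone has to choose the rule outside the plan, possibly after Year 2 results are known.

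**Working it through.** **1. Status of a cancer found at the second study round**

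| Provision | Status |
|---|---|
| 8.1.2, last sentence | Negative for Year 1; counted in Year 2 |
| 8.2.2, first positive criterion | Positive for Year 2 (tissue obtained after the Year 2 screen and before the next annual screen) |
| 8.2.2, closing sentence | Negative for Year 2 |

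The second and third rows cannot both hold, and the third also contradicts the first.

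**2. Does another section settle it?**

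Section 8.3 does not. It says "A FP test result will be defined as a positive test score on a patient with a negative reference standard", and it also requires a positive reference standard for a true positive. Yet it says that an exam on a patient with at least one cancer can only be a true positive or a false negative. A Year 2 screen-detected cancer that the closing sentence has made negative fits both descriptions.

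Footnote d does not settle it either. It uses one label for two events, and the closing sentence does not carry the d mark. The first criterion calls the next annual screen Year 2 as well, so its window literally runs from Year 2 to Year 2. The second positive criterion, which carries the mark, does work once its marked term is read as the off-study screen. The stray Y0 in footnote c fits the same explanation: the years were renumbered and the change was not completed.

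**3. Size under each reading**

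The plan gives no Year 2 accuracy figure to reproduce, and no Year 2 sample size, cancer rate or DBT recall rate. The inputs below are therefore assumptions, some borrowed from other parts of the document.

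- N = 2631, the Year 1 requirement in section 8.7. That figure reproduces: with rates 0.001 and 0.004 and one-sided alpha 0.025, the exact binomial test has critical value 7, actual alpha 0.0181 and power 0.9001.
- Screen-detected rate for DBT plus MBI: 3, 5 or 8.8 per 1000. The first two are assumed. The third is the invasive rate for 2D mammography plus MBI in section 8.7.
- Later-diagnosed cancers: 0.89 per 1000, from section 8.6 item 5 ("the interval cancer rate among women with dense breasts was 89 per 100,000 women").
- Recall among women without cancer: 6.6% (the rise in recall from adding MBI, section 1.4) to 15% (assumed).

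Let D be the screen-detected cancers, L the later-diagnosed cancers, H = N − D − L the women without cancer, and f the recall rate among them. Every D is positive on the combination. L = 2631 × 0.00089 = 2.34, taken first as all test negative at Year 2.

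Under the first criterion:
- sensitivity = D/(D + L)
- specificity = 1 − f
- PPV1 = D/(D + fH)

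Under the closing sentence:
- sensitivity = 0/L = 0
- specificity = 1 − (fH + D)/(H + D)
- PPV1 = 0

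| | 3 per 1000 | 5 per 1000 | 8.8 per 1000 |
|---|---|---|---|
| D = women changing status | 7.9 | 13.2 | 23.2 |
| Sensitivity, first criterion | 0.771 | 0.849 | 0.908 |
| Sensitivity, closing sentence | 0 | 0 | 0 |
| PPV1, first criterion, f = 6.6% | 0.044 | 0.071 | 0.119 |
| PPV1, first criterion, f = 15% | 0.020 | 0.032 | 0.056 |
| PPV1, closing sentence | 0 | 0 | 0 |
| Specificity, f = 6.6%: first criterion → closing sentence | 0.934 → 0.931 | 0.934 → 0.929 | 0.934 → 0.926 |
| Specificity, f = 15%: first criterion → closing sentence | 0.850 → 0.847 | 0.850 → 0.846 | 0.850 → 0.843 |

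**4. Variation**

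Some later-diagnosed cancers may already have been test positive at Year 2, for example category 3 lesions sent to 6-month follow-up MBI under section 5.3. If a quarter were, sensitivity under the first criterion is (D + 0.25L)/(D + L) = 0.828, 0.887 or 0.931. Under the closing sentence it is 0.25L/L = 0.25, and PPV1 = 0.25L/(D + 0.25L + fH), which is 0.1% to 0.3%.

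**The case against.** The strongest reply is that the intent can be recovered. The closing sentence of 8.2.2 stands where the corresponding sentence of 8.1.2 stands, and that one moves a cancer found at the next screen out of the current year. By analogy, 8.2.2 meant the off-study screen. The missing footnote mark proves little, since the parallel sentence in 8.1.2 lacks its mark too. A combined sensitivity near zero would be noticed at once, so silent bias in a report is unlikely.

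The inputs are also rough. The 6.6% is an increment over mammography, not the total recall of the combination, so the upper PPV1 values are probably too high. The 8.8 per 1000 comes from a study with 2D mammography and is applied here to a repeat round with DBT. The 0.89 per 1000 is a published interval cancer rate for women with dense breasts, not a miss rate for DBT plus MBI. Year 2 N may fall below 2631, because section 5.1 does not require Year 2 DBT while the analysis set in 8.4 needs both exams.

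All of this is fair, and it limits how much weight the intermediate figures can bear. It does not remove the contradiction. The intended rule is an inference, and the text of a reference standard should not need one. The drop in sensitivity and PPV1 to about zero comes from the definition and hardly depends on the inputs.

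**Conclusion.** The concern holds. Section 8.2.2 contradicts itself and section 8.1.2, and neither 8.3 nor the footnotes resolve the conflict. The numerical consequence is conditional on the closing sentence being applied over the other two provisions. Under the stated assumptions, about 8, 13 or 23 women would change status, combined Year 2 sensitivity would fall from 77% to 91% down to 0% (or from 83% to 93% down to 25% in the variation), and PPV1 would fall from 2.0% to 11.9% down to 0% (0.1% to 0.3% in the variation). Specificity would fall by only 0.3 to 0.8 percentage points. The overstatement of NPV for DBT alone is clear in direction but is not quantified here.

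The reach is limited to the status-based Year 2 measures in secondary endpoint 2. The primary endpoint, sample size, Year 1 comparisons, recall and biopsy rates, PPV3, advanced cancer rate and interval cancer rate are not affected. It should be corrected before the Year 2 analysis.

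**What to change.** - Give the off-study screen that follows Year 2 its own label, for example *Year 3 clinical screen*. Use it in the first positive criterion of 8.2.2, in every term marked d, in footnote d and in the closing sentence.
- Reword the closing sentence along these lines: *a woman whose cancer is detected on the Year 3 clinical screen is taken as negative for Year 2.*
- State explicitly that a cancer detected at study Year 2 screening is positive for Year 2.
- In footnote c, replace Y0 with Year 1.

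This changes wording in 8.2.2 and footnotes c and d only. It needs no new data and leaves sample size and study conduct as they are.

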8.1.3 Participants Not Meeting Reference Standard Definitions

If a participant does not meet either definition for Positive or Negative Breast Cancer Status in a given screening year, for instance a participant who has no known breast cancer diagnosis but has no information available via chart review and cannot be contacted, will be considered “lost to follow up” and assumed to not have breast cancer in the analysis. In the event of a participant’s death, the date of death and cause of death will be recorded to determine if breast cancer was diagnosed and the length of follow up.

^aThe date of histopathologic breast cancer diagnosis is defined as the date on which tissue was obtained via biopsy or surgical excision, and subsequently determined to include invasive cancer (with or without DCIS) or DCIS.

^bYear 1 screening is defined as having both Year 1 MBI and Year 1 DBT. If not performed on the same day, the date of Year 1 screening is the day Year 1 MBI is performed.

^cYear 2 screening is targeted to be performed with both MBI and DBT approximately 365 days (target range 335 – 455 days) after Year 1 screening MBI. For purposes of establishing breast cancer status of Screening Year 1, Year 2 screening may be performed with any combination of breast imaging tests, most often including MBI, DBT, or both, but may also include breast MRI, WBUS, or CEDM; testing may be performed for either screening or diagnostic indications. The date of Year 2 screening used for reference standard is the earliest of these tests performed at least 335 days after Y0 screening.

^dYear 2 screening is not conducted as part of the research study, but considered for purposes of establishing Year 2 breast cancer status as any documentation of breast imaging (MBI, DBT, MRI, WBUS, or CEDM) performed within 335 – 455 days after Year 2 screening.

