7. DURATION OF FOLLOW-UP

Study participation involves 2 study visits for breast screening – one at the beginning of the study and a second visit one year later. Participants will be enrolled in the study for approximately 2.5 years (30 months) to ascertain breast cancer status, and may be contacted at the end of study if breast cancer status cannot be ascertained based on chart review, alone. If only one of the baseline

imaging tests (DBT or MBI) is completed, the patient will be excluded from the study and no data will be collected. Participant's breast cancer status will be obtained from chart review or patient contact targeted for 365 days after each screening year, but may be obtained from 335 days to 455 days after screening, unless the patient specifically requests to withdraw from the study. If a patient is diagnosed with a primary breast cancer during the study period, no subsequent follow-up or further study imaging will be required for this research study.

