8.4 Definition of Analysis Set

The Analysis Set for each screening year will be defined as the subset of enrolled patients who met eligibility criteria and completed screening imaging with both DBT and MBI.

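### Footnote c lets symptom-driven imaging from day 335 close Year 1, so a cancer missed by both tests can be scored true negative on both; a small upward bias in absolute sensitivity

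*Combined protocol and SAP*

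**What the plan says.** Section 8.1.2 gives two routes to positive status for Year 1. Rule 1 needs a tissue diagnosis after Year 1 screening and before Year 2 screening. Rule 2 covers a woman with no Year 2 screening whose cancer is diagnosed "within 365 days of Year 1 screening". Both rules refer to footnote c for what Year 2 screening means.

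Footnote c, at the end of section 8.1.3, widens the term for this purpose to any combination of breast imaging tests, and "testing may be performed for either screening or diagnostic indications". It sets the date as follows: "The date of Year 2 screening used for reference standard is the earliest of these tests performed at least 335 days after Y0 screening". Y0 is not defined; I read it as Year 1 screening. Footnote a dates a diagnosis by the day tissue was obtained.

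Two provisions cover a woman who meets neither positive rule. Section 8.1.2 closes by treating a cancer detected on Year 2 screening as Year 1 negative: "the cancer diagnosis is included in the Year 2 analysis, not the Year 1 analysis". Section 8.1.3 says that anyone who fits neither status definition is "assumed to not have breast cancer in the analysis".

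Three further rules matter. Section 8.3: "A TN test result will be defined as a negative test score on a patient with a negative reference standard". Section 8.4 limits each year's analysis set to eligible women who "completed screening imaging with both DBT and MBI". Section 7 says that after a breast cancer diagnosis "no subsequent follow-up or further study imaging will be required for this research study".

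**The concern.** The Year 1 interval exists partly to catch cancers that both screening tests missed. Footnote c allows the very imaging that reveals such a cancer to end that interval. From day 335, a woman who presents with a lump is then handled as if she had attended her next annual screen, and the false negative disappears.

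At stake is the absolute Year 1 sensitivity of DBT, MBI and the combination (section 8.6 item 2). Any error runs one way, because the rule can only take missed cancers out of the denominator. The plan may also contradict itself: section 8.6 item 5 defines an interval cancer as one diagnosed between the two screening rounds but not at study imaging. The same woman can therefore be an interval cancer in that item and cancer-free in the sensitivity analysis.

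**Working it through.** **Following one case through the rules.** Take a woman negative on both Year 1 tests, with symptom-driven imaging on day 345 and a malignant biopsy on day 347.

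1. Footnote c makes day 345 her Year 2 screening date.
2. Rule 1 fails, because day 347 is not before day 345.
3. Rule 2 fails. Day 347 is within 365 days, but she is deemed to have had Year 2 screening.
4. The closing sentence of section 8.1.2, or failing that the default in section 8.1.3, makes her Year 1 negative.
5. Section 8.3 then scores both tests true negative.
6. Her cancer is assigned to Year 2, but she enters that analysis set only if she completes both Year 2 exams, which section 7 no longer requires of her.

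**Window.** Before day 335 no imaging can close Year 1. After day 365, a diagnosed woman with no Year 2 screen falls outside rule 2 in any case. The problem is therefore confined to about days 335 to 365.

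**Inputs from the plan.** Evaluable N = 2631, DBT invasive detection 4.7 per 1000 and incremental detection 4 per 1000 (section 8.7); interval cancer rate about 0.9 per 1000 (section 8.6 item 5).

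**The plan's own figures first.** For the exact binomial test of 0.001 against 0.004 at N = 2631, P(X ≥ 7 | 0.001) = 0.0181 and P(X ≥ 6 | 0.001) = 0.0513, so the critical count is 7. Power is P(X ≥ 7 | 0.004) = 0.9001, which agrees with section 8.7. The interval-cancer threshold of 7 also reproduces at 2631: the Clopper-Pearson lower bound is 1.07 per 1000 for 7 cancers and 0.84 for 6.

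**Cancers expected in the window.** Missed cancers per year: 0.0009 × 2631 = 2.37.

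| Assumption | Share of the year | Expected cancers | P(at least one) = 1 − exp(−mean) |
|---|---|---|---|
| 7-day imaging-to-biopsy lag; 87% not yet attended Year 2 | 23/365 × 0.87 = 0.055 | 0.13 | 12% |
| Uniform timing | 30/365 = 0.082 | 0.19 | 18% |
| Linearly rising hazard | 1 − (335/365)² = 0.158 | 0.37 | 31% |

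The last two rows assume that every cancer diagnosed in the window followed imaging done from day 335, and that all 2631 women are still unscreened. The 87% in the first row assumes Year 2 visits spread evenly over days 335 to 455: at day 350, 15/120 = 12.5% have attended.

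**Effect on sensitivity (illustrative).** Detected by the combination: (4.7 + 4)/1000 × 2631 = 22.89, taking no detected DCIS.

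- Nothing dropped: 22.89/(22.89 + 2.37) = 90.6%.
- 0.13 dropped: 22.89/(22.89 + 2.24) = 91.1%.
- 0.19 dropped: 22.89/(22.89 + 2.17) = 91.3%.
- 0.37 dropped: 22.89/(22.89 + 1.99) = 92.0%.
- One whole cancer dropped: 22.89/(22.89 + 1.37) = 94.4%.

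For scale, the exact 95% interval at 23 of 25 is 74% to 99%. NPV moves by 0.19/2631, about 0.007 percentage points.

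**What does not move.** DBT and MBI sensitivity share one denominator, so removing a cancer that both missed leaves their ratio unchanged. Such a cancer adds nothing to either detection count in the primary comparison.

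**The case against.** Negative status is less explicit than the chain above suggests. None of the four negative rules in section 8.1.2 fits a woman with proven cancer. The closing sentence of that section carries no footnote mark and could mean the ordinary study screen. The default in section 8.1.3 is written around women lost to follow-up. Section 8.3 also calls a pathology-proven cancer without a matching finding occult. All this shows loose drafting, but none of it gives a route to positive status: the occult rule sits under the definition for women who already have a positive reference standard.

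A reader might infer that the cancer vanishes from the trial. The documents do not support that. Footnote c confines its wide definition to Year 1 breast cancer status, and section 8.6 item 5 most plainly still counts her. She could also complete both Year 2 exams. Section 8.2.2 does not settle her place in Year 2, because it uses the same label for the Year 2 screen and the one after it.

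A reader might also infer a threat to the primary endpoint through a Year 1 MBI-positive cancer proven late. That needs an unstated reading of section 8.5 and a late work-up. The only delayed step in section 5.3 is a 6-month follow-up MBI, well before day 335. I do not rely on it.

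The objection on size largely stands. The 0.19 and 0.37 figures are near upper bounds under their timing assumptions, because women already screened leave the risk set and some biopsies in the window follow imaging done before day 335. The 0.9 per 1000 rate is a mammography benchmark, and these cancers must be missed by MBI as well.

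**Conclusion.** The point holds as a minor one. Read literally, footnote c and section 8.1.2 turn a cancer missed by both tests and found through symptoms on days 335 to 365 into two true negatives, and may leave it out of both years' accuracy analyses. The bias is secondary and always favours absolute sensitivity. At 0.9 per 1000 and N = 2631, 0.13 to 0.19 cancers are expected, up to 0.37 with a linearly rising hazard. The average shift in illustrative combined sensitivity is about 0.5 to 0.7 points, or 1.4 points in the rising-hazard case, well inside the sampling error. If one such cancer does occur, the shift is 3.8 points (90.6% to 94.4%). These figures rest on the mammography benchmark, the assumed timing, the planned detection rates and no detected DCIS. They do not support any claim that the primary result or the relative sensitivity of DBT and MBI is biased.

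**What to change.** In footnote c, state that imaging prompted by new breast symptoms or clinical signs, or done as work-up of a Year 1 finding, does not count as Year 2 screening when the two Year 1 positive rules are applied, whatever its result. Routine annual exams count even if coded diagnostic, and so does imaging of unknown indication. The rule then depends on why the exam was done and not on what it found, and an annual screen under a diagnostic code does not become a Year 1 miss. Symptom-driven or work-up imaging with negative or benign results can still document negative status under negative rule 2 of section 8.1.2.

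Leave both positive rules otherwise as they are: rule 1 without a 365-day limit, rule 2 with it. The woman in the example then has no Year 2 screening, meets rule 2, and is a false negative on both tests. In section 8.6 item 5, state that the interval ends at the Year 2 screening date as so defined, so that the interval-cancer and sensitivity analyses agree.

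The cost is a few sentences of wording and abstracting the reason for each breast imaging exam from day 335. Absolute sensitivity may look slightly less favourable.
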